6.6 Safety Analyses

6.6.1 Treatment-emergent Adverse Events

Summaries and analyses of treatment-emergent adverse events (TEAE) are the same as specified in the M-SAP with the following revisions.

TEAEs are defined as those adverse events with onset dates in the interval from treatment initiation to either the Final Safety Visit if completed, the date of death if the participant dies, 40 days after last study contact if the participant early terminates or is lost to follow-up, or the date of first dose of study drug during participation in the OLE, if so exposed. The interval is inclusive except for adverse events that occur on the day of treatment initiation and are known to precede first exposure to study drug.

In addition to summaries specified in the M-SAP, TEAEs will be summarized by Medical Dictionary for Regulatory Activities (MedDRA) system organ class and preferred term for fatal TEAEs, TEAEs that occurred during a participant's COVID-19 infection (defined as 5 days prior to symptom onset to end of COVID-19 symptoms or end of double-blind follow-up, if ongoing), and TEAEs and serious TEAEs stratified by the following subgroups: baseline riluzole use, baseline edaravone use, age, sex, race, ethnicity, weight, BMI, and CKD stage. Subgroup classifications will be the same as described in Section 6.5.12 Subgroup Analyses except that the "other" group will be retained regardless of prevalence.

Treatment-dependent differences in the proportion of participants experiencing a given type of TEAE will not be tested. Treatment-dependent differences in TEAE incidence rates will be estimated as differences rather than ratios and will include comparison-wise 95% confidence intervals with variance estimates obtained by the delta method.

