The incidence and rate (events/participant years) of AEs in the pridopidine 45 mg BID group (n=981, participant years= 1091) and placebo group (n=338, participant years=148.8) was evaluated across the integrated safety analysis of the 22 trials.

The integrated analysis of safety data from the 22 pridopidine clinical studies, primarily conducted in Huntington Disease (HD) participants, indicated that the adverse events (AE) profile of the 45 mg BID dose is generally comparable with that of placebo. Pooled analysis suggests no increased risk of cardiac toxicity, exacerbation of psychiatric complications, or suicidality attributed to the 45 mg BID dose.

Over all in the integrated dataset, the rate of participants reporting at least 1 AE was similar between the placebo group (rate=2.35 events/participant year) and the pridopidine 45 mg BID group (rate =1.81 events/participant year). Most AEs for participants in both the placebo and pridopidine 45 mg BID groups were reported as mild or moderate in severity. Severe AEs occurred with a similar frequency across treatment groups.

Serious adverse events (SAEs) were observed across both active and placebo groups. There was a slight increase in the number of participants with SAEs in the active groups compared with the placebo group, but no dose-dependence was observed (detailed in the IB safety section).

AEs indicating Proarrhythmic Potential

Across the integrated safety database (22 trials), the rate (events/participant year) of AEs of QT prolongation was higher in the placebo group (rate=0.013 events/participant year) compared to the pridopidine 45 mg BID group (rate=0.005 events/participant year) (Table 1).

The 52-week placebo-controlled PRIDE-HD study included 5 treatment arms: placebo, pridopidine 45 mg BID, pridopidine 67.5 mg BID, pridopidine 90 mg BID, and pridopidine 112.5 mg BID. The AE data from this trial provides a more sensitive analysis of dose-dependency and is thus analyzed separately. The number of participant-years of exposure was similar in each of the treatment groups in this study; therefore, only tables of AE incidence were generated.

In the PRIDE-HD trial, there was a higher overall incidence of AE-reports of QT prolongation (unrelated to any other proarrhythmic event) in pridopidine-treated participants compared to placebo-treated participants: 1.5% in pridopidine-treated participants vs 0% in placebo-treated participants. However, there was no evidence of dose-response (Table 2).

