 - For participants taking Nuedexta, the Nuedexta dose should be taken within 6 hours before the ECG
- If QTcF meets Stopping/Monitoring Rules, then ECG will be repeated twice² and the QTcF will be determined by the average of the 3 ECGs.
- If the average QTcF meets Stopping Rules, IP will be stopped, and a follow-up ECG will be performed as soon as practicable (but at least 2 days after stopping IP) to ensure recovery from QT-prolongation.

ECG Monitoring Flow at Week 24 for Participants who choose to Enroll into the OLE

- Baseline QTcF for the purpose of OLE will be measured by **a mean of 3 (triplicate)** 12-lead **pre-dose** ECG assessments
 - Three 10-second ECG recordings should be performed, with at least one minute in between each ECG recording. QTcF will be automatically calculated by the ECG machine, and will be copied onto source documents. Mean QTcF from the three ECG recordings will be calculated manually and used as Baseline pre-dose QTcF for the OLE. The SI should review and confirm the mean QTcF.
- For participants taking Nuedexta, the Nuedexta dose should be taken within 6 hours before the ECG.
- If the mean QTcF is >450 ms for men and >470 ms for women at the Week 24 Visit, then participant will not be eligible to continue into the OLE.
- The OLE IP should then be administered to the participant, and **a single** 10-second ECG should be collected 1-2 hours after administration of the OLE IP.
- If QTcF meets Stopping/Monitoring Rules then ECG will be repeated twice² and the QTcF will be determined by the average of the 3 ECGs.
- If the mean QTcF meets Stopping Rules, IP will be held , and a follow-up ECG will be performed as soon as practicable (but at least 2 days after stopping IP) to ensure recovery from QT-prolongation.
- If the mean QTcF meets Monitoring Rule, participant may continue on IP per-protocol and have another ECG after 3 -14 days.
- If a participant meets the Monitoring Rule for the second time, the participant may decrease to QD dosing for the remainder of the study.
- A follow-up ECG should occur 3-14 days after decreasing to QD dosing. If the participant meets the monitoring rule during this follow-up ECG, the participant must discontinue IP immediately.

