6.1.8 Week 24 Visit or Early Termination Visit

Participants Not Enrolling into the OLE

Only a pre-dose ECG is required at this visit for participant who are not enrolling into the OLE.

If a participant's visit occurs in the morning, the participant should be instructed not to take the morning dose at home, and the morning dose should be administered in-clinic after the pre-dose ECG. If a participant's visit occurs in the afternoon, the participant should be instructed to take the morning dose immediately upon waking in the morning, and the second dose should be taken after the pre-dose ECG.

Participants Enrolling into the OLE

A pre-dose and post-dose ECG are required for participants who enroll into the OLE. The SI should confirm the mean QTcF following the pre-dose triplicate ECG. If the mean QTcF is >450 ms for men and >470 ms for women, then participant will not be eligible to continue into the OLE.

If a participant's visit occurs in the morning, the participant should be instructed not to take the morning dose at home. A pre-dose triplicate ECG should be collected prior to administration of the first dose of OLE IP in-clinic. A single post-dose ECG should then be collected 1-2 hours after administration of the first dose of OLE IP.

If a participant's visit occurs in the afternoon, the participant should be instructed to take the morning dose immediately upon waking in the morning, and a pre-dose triplicate ECG should be collected prior to administration of the first dose of OLE IP in-clinic (which will be the 2nd daily dose).

A single post-dose ECG should then be collected 1-2 hours after administration of the first dose of OLE IP.

This visit will take place on Day 168 ± 7. The following procedures will be performed at either the Week 24 Visit or the Early Termination Visit:

- Home Spirometry
- ALSAQ-40
- CNS-BFS
- CNS-LS
- **Triplicate** ECG monitoring **BEFORE** IP administration
- Administer **single** ECG 1-2 hours **AFTER** IP is administered (only for participants enrolling into the OLE)
 - Note: if the participant is taking Nuedexta, the Nuedexta dose should be taken within 6 hours prior to the pre-dose ECG. If participant has taken Nuedexta outside of this window, the ECG should still be completed and a protocol deviation recorded. Refer to the MOP for additional guidance.
- Plasma PK collection
 - **after** the pre-dose ECG for participants NOT participating in the OLE

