6.2 Open Label Extension

Participants who completed the placebo-controlled portion of the trial on drug, will be eligible to continue in the OLE as outlined in the SOA. Participants will first be asked about their desire to continue in the OLE at the Regimen-Specific Screening Visit. They will also be asked to *re-confirm* whether they want to continue in the OLE at the Week 16 Visit of the placebo-controlled period. In the OLE, pridopidine will be provided by Prilenia Therapeutics, until the primary results of the 24 week double-blind portion of the study are available, or they terminate development of pridopidine for ALS.

To preserve the blind, all participants in the OLE, regardless of whether they were in the active or placebo arm of the study initially will need to initiate the OLE at a QD dose and then up-titrate to BID after 2 weeks.

Modifications to OLE Schedule

Designated visits in the Schedule of Activities for the OLE (i.e. Week 8, Week 16) may be conducted via telemedicine (or phone if telemedicine is not available) with remote services

instead of in-person if needed to protect the safety of the participant due to a pandemic or other reason. If a planned in-clinic visit is conducted via telemedicine (or phone if telemedicine is not available) with remote services, only selected procedures will be performed. Instructions on how to document missed procedures are included in the MOP.

In addition to the procedures in the Master Protocol that should be conducted during the phone or telemedicine and remote visits, the following regimen-specific procedures should be completed:

- Home Spirometry
- CNS-BFS
- CNS-LS
- ALSAQ-40

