- ¹³ If the CSF collection is unable to be performed for logistical reasons, such as scheduling, at the Week 16 Visit, it may be performed at the Week 24 Visit.
- ¹⁴ If a participant's visit occurs in the morning, the participant should be instructed that the morning dose of study medication should not be taken, and the morning dose should be administered in-clinic 1-2 hours prior to the POST-DOSE ECG. If a participant's visit occurs in the afternoon, the participant should be instructed to take the morning dose immediately upon waking in the morning, and the second dose should be administered in-clinic 1-2 hours prior to the POST-DOSE ECG.
- ¹⁵ At the regimen-specific Screening visit (and Week 24 for participants enrolling in OLE), QTcF will be determined by the mean of three, 10-second recordings of a 12-Lead ECG (performed at least 1 minute a part) BEFORE IP administration. For participants on Nuedexta, the Nuedexta dose should be taken within 6 hours BEFORE the ECG, refer to the MOP for additional guidelines.
- ¹⁶ At Baseline and Week 4 (and Week 24 for participants enrolling in OLE) QTcF will be determined by a single 10-second 12-lead ECG, 1-2 hours AFTER IP administration. If stopping or monitoring rules are met, refer to Section 4.4. For participants on Nuedexta, the Nuedexta dose should be taken within 6 hours BEFORE the ECG, refer to the MOP for additional guidelines.
- ¹⁷ For participants that will NOT be enrolling into the OLE, QTcF will be determined by a single 10-second 12 lead ECG BEFORE administration of the IP. If stopping or monitoring rules are met, refer to Section 4.4. For participants on Nuedexta, the Nuedexta dose should be taken within 6 hours BEFORE the ECG, refer to the MOP for additional guidelines.
- ¹⁸ IP must be administered at Week 4 (and Week 24 for participants enrolling into the OLE) 1-2 hours prior to the POST-DOSE ECG.

¹⁹ Visit may be conducted via phone or telemedicine with remote services instead of in-person if this is needed to protect the safety of the participant due to a pandemic, or other reasons.

²⁰ If required due to pandemic-related restrictions, Forced Vital Capacity (FVC) performed by a Pulmonary Function Laboratory evaluator or with a study-approved home spirometer, or sustained phonation using a study approved method may be used for eligibility (Master Protocol Screening ONLY).

²¹ All blood draws should occur after the ECG is collected, or at least 1 hour prior to the ECG.

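### The TEAE window includes the whole day of the first open-label dose, so a former placebo participant's event after that dose counts as a placebo TEAE (minor wording correction)

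*SAP*

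**What the plan says.** SAP 6.6.1 places events by date: "TEAEs are defined as those adverse events with onset dates in the interval from treatment initiation" to one of several end points. For OLE entrants the end point is "or the date of first dose of study drug during participation in the OLE, if so exposed". On the boundaries it says: "The interval is inclusive except for adverse events that occur on the day of treatment initiation and are known to precede first exposure". It states no other exception.

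The visit flow around that end date is as follows.

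- Protocol 6.1.8 gives the first OLE dose in clinic at the Week 24 visit, after a pre-dose triplicate ECG. It continues: "A single post-dose ECG should then be collected 1-2 hours after administration of the first dose of OLE IP".
- SAP 2.9, footnote 16, has the same ECG in the placebo-controlled schedule. After naming Baseline and Week 4 it adds "and Week 24 for participants enrolling in OLE) QTcF will be determined by a single 10-second 12-lead ECG, 1-2 hours AFTER IP administration".
- Protocol 6.2 says "all participants in the OLE, regardless of whether they were in the active or placebo arm of the study initially will need to initiate" on the once-daily schedule. Protocol section 3 confirms that the OLE drug is pridopidine.
- Protocol 4.4 bars entry if the mean pre-dose QTcF is above 450 ms for men or above 470 ms for "women at the Week 24 Visit, then participant will not be eligible to continue into the OLE".

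**The concern.** The two ends of the window are treated differently. On the first day, an event known to come before study drug is left out. On the last day, an event known to come after open-label pridopidine is kept in.

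For a former active participant this does little harm, because the event still sits under pridopidine. For a former placebo participant it puts an event that followed active drug into the placebo column. Any effect of the first dose would therefore be misassigned in one direction only.

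The day is also one of targeted cardiac observation. Protocol 1.1.2 gives a median time to peak concentration of 1.25-2 hours, so an ECG at 1-2 hours falls near the peak. QT prolongation is the regimen-specific safety endpoint (SAP, Safety Endpoints). For a former placebo entrant, one of the three scheduled post-dose ECGs (Baseline, Week 4, Week 24) follows pridopidine.

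The outputs at stake are the TEAE tables and the estimated differences in TEAE incidence rates with their 95% confidence intervals. No efficacy analysis is involved.

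**Working it through.** The plan gives no figure of its own to reproduce here. The check is a reading of the rule, followed by a size estimate.

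**Reading.** Let a former placebo participant take the first OLE dose on day D and have an event that begins later on day D.

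1. The onset date lies between treatment initiation and D, and the interval includes D.
2. The one exception covers events before first exposure on the initiation day. This event meets neither condition.
3. The safety set in SAP 6.1 classifies participants by treatment actually received. It gives no rule for moving a single event after one OLE dose.

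The event is therefore a double-blind TEAE under placebo.

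**Inputs for size.**

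- Window: Day 0 to Day 168, which is 169 days counted inclusively (SAP 2.9).
- Placebo arm: 40 participants (Protocol, RSA summary).
- Former placebo entrants to the OLE: 75-90% of 40 = 30-36. This is an assumption, because the documents give no figure.
- Pooled adverse event rates from Protocol 1.1.2: "placebo group (rate=2.35 events/participant year) and the pridopidine 45 mg BID group (rate =1.81 events/participant year". QT prolongation at 45 mg BID is 0.005 per participant-year (Table 1).
- Events occur at a constant rate over time. This is also an assumption.

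**Results.**

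| Quantity | Calculation | Result |
|---|---|---|
| Share of window | 1/169 | 0.6% |
| Entrant time on that day | 30/365.25 to 36/365.25 | 0.0821 to 0.0986 participant-years |
| Any AE at the 45 mg BID rate | 1.81 × 0.0821 to 1.81 × 0.0986 | 0.15 to 0.18 events |
| Any AE at the placebo rate | 2.35 × 0.0821 to 2.35 × 0.0986 | 0.19 to 0.23 events |
| QT prolongation AEs | 0.005 × 0.0821 to 0.005 × 0.0986 | 0.0004 to 0.0005 events |
| Regimen-only placebo time, if all complete | 40 × 169/365.25 | 18.5 participant-years |
| Contribution to the placebo TEAE rate | 0.149/18.5 to 0.178/18.5 | 0.008 to 0.010 per participant-year |
| Relative to 2.35 | 0.0096/2.35 | about 0.4% at most |

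Under the constant rate these are upper limits, because day D also includes the hours before the dose. The visit window of ±7 days does not change the share: 1/162 to 1/176 is still about 0.6%.

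The 0.4% is the total contribution of that day, not a bias. The net difference from a day on placebo, at the pooled rates, is (1.81 − 2.35) × 0.0821 to (1.81 − 2.35) × 0.0986 = −0.044 to −0.053 events. Divided by 18.5 this is −0.0024 to −0.0029 per participant-year, about 0.1% of 2.35. The pooled rates thus give no sign of an inflated placebo column.

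**The case against.** The strongest reply is that nothing would change. The expected count is a fraction of one event, TEAE proportions are not tested, and neither the primary analysis nor the futility rule uses the TEAE window. At the pooled rates the net effect is smaller still and runs opposite to an inflated placebo rate. All of this stands, and it is why the point is minor.

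The QT example is also limited. A QT finding is not automatically an adverse event. Results against the stopping and monitoring rules are summarised under SAP 6.6.3, which the proposed edit does not touch. Protocol 4.4 already resets the QTcF baseline for OLE entrants. Entrants have passed the QTcF limit, and the predicted effect at 45 mg BID is 6.6 ms with an upper bound of 8 ms. A threshold crossing after one dose is unlikely. It remains possible, however, and the rule misplaces any event after the dose, cardiac or not.

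Including Week 24 has a purpose, since it captures events found at that visit before the OLE dose. The correction keeps those events.

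The master SAP was not available and could hold a supplementary timing convention. SAP 6.6.1, however, states this interval as a revision to the master SAP, and SAP section 1 makes the regimen SAP prevail where they differ. Only an attribution rule compatible with 6.6.1 could alter the result.

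Two practical objections concern the fix. First, it takes events out of the numerator and leaves person-time alone. The time involved is at most 0.0986/18.5 = 0.5% of the placebo total, so either treatment of it is negligible. Second, the documents do not show that onset time relative to the OLE dose is recorded. The existing start-day exception needs the same kind of information, and events of unknown order would simply stay where they are.

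**Conclusion.** The concern holds. SAP 6.6.1 as written counts a former placebo participant's event after the first open-label pridopidine dose, on the same date, as a double-blind placebo TEAE. This is a stated rule that gives the wrong column, not a missing detail.

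The effect is very small: one day in 169, and 0.15-0.18 expected events of any kind across the regimen's placebo entrants. These figures rest on the assumed 30-36 entrants, on a constant event rate, and on pooled rates drawn mainly from Huntington disease studies. A true first-dose effect could exceed a constant rate, but the documents give no figure for one. No efficacy or futility conclusion is affected.

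**What to change.** Extend the boundary sentence in SAP 6.6.1 so that the exception works at both ends, by adding: *and except for adverse events that occur on the day of the first OLE dose and are known to follow that dose.*

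Apply it to both arms and report the excepted events with the OLE data. Events that day whose order relative to the dose is unknown stay in the double-blind window, as the start-day rule already implies. Leave the other end dates as they are.

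The cost is one clause. No new visits or assessments are needed: the pre-dose and post-dose ECGs are already taken that day, and the start-day exception already requires the order of event and dose.

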MAM	Mitochondria-associated membrane
MATE1	Multi Drug and Toxin Extrusion Protein 1
MATE2-K	Multi Drug and Toxin Extrusion Protein 2-K
MN	Motor Neuron
MOP	Manual of Procedures
mHTT	Mutant Huntingtin
NMJ	Neuromuscular Junction
OLE	Open Label Extension
OCT1	Organic Cation Transporter 1
OCT2	Organic Cation Transporter 2
QD	Once Daily
PD-LID	Parkinson's Disease-Levodopa Induced Dyskinesias
PET	Positron emission tomography
PO	By Mouth
PPK	Population Pharmacokinetic Model
PM	Poor Metabolizer

PY	Participant-Years
QTcF	Fridericia-corrected QT
RSA	Regimen-Specific Appendix
S1R	Sigma-1 Receptor
SAE	Serious Adverse Event
SI	Site Investigator
SOA	Schedule of Activities
SVC	Slow Vital Capacity
TDD	Total Daily Dose

REGIMEN-SPECIFIC APPENDIX (RSA) SUMMARY

Regimen-Specific Appendix D

For pridopidine 45 mg oral capsule administered twice daily (BID) or its matching placebo.

Rationale and RSA Design

The proposed study is based on cumulative preclinical and clinical studies that demonstrate that pridopidine acts primarily as a Sigma-1 Receptor (S1R) agonist and demonstrates neuroprotective properties mediated by S1R. The purpose of this study is to evaluate the effect of pridopidine 45 mg BID on ALS functional decline, specifically bulbar, upper and lower limb, and respiratory function in participants with ALS.

Allocation to Treatment Regimens

Participants must first be screened under the Master Protocol before they are randomized to a regimen.

As soon as pre-defined criteria for futility for the regimen are met, or the target number of randomized participants has been reached, enrollment will stop in the regimen.

Number of Planned Participants and Treatment Groups

The number of planned participants for this regimen is approximately 160.

There are 2 treatment groups for this regimen, active and placebo. Participants will be randomized in a 3:1 ratio to active treatment or placebo (i.e., 120 active: 40 placebo).

Planned Number of Sites

Research participants will be enrolled from approximately 60 centers across the US.

Treatment Duration

The maximum duration of the placebo-controlled treatment period is 24 weeks.

Follow-up Duration

At the conclusion of the 24-week placebo-controlled treatment period of the study, all participants will either schedule a 28-day follow up phone call and end their participation in the regimen or have the option to receive pridopidine in the Open Label Extension (OLE) period of the study.

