5.11 Pridopidine Known Potential Risks and Benefits

5.11.1 Known Potential Risks

QT prolongation:

In the PRIDE-HD trial of 408 participants, the cardiac effects of pridopidine were evaluated in people with HD at doses up to 112.5 mg BID for 52 weeks. Although low, there was a higher overall incidence of AE-reports of QT prolongation in pridopidine-treated participants compared to placebo-treated participants: 1.5% in pridopidine-treated participants vs 0% in placebo-treated participants. However, there was no evidence of a dose response in QT-related AEs (QT prolongation AEs: 0 in placebo, 2 in 45 mg BID, 0 in 67.5 mg BID, 1 in 90 mg BID and 2 in 112.5 mg BID; total 5/327=1.5%). Using the PRIDE-HD data, a cardiac exposure-response model was developed utilizing ECG data paired with PK samples collected for up to a year. Only ECGs that were paired with PK samples (n=3071) were used to develop the cardiac exposure-response model, which was based on 2753 ECGs from pridopidine-treated participants and 763 from placebo-treated participants.

A concentration-dependent effect of pridopidine on the QTcF interval was observed in this study, with a slope of 0.012 ms per ng/mL (90% CI: 0.0109 to 0.0127 ms per ng/mL).

At 45 mg BID, the predicted QT effect ($\Delta\Delta\text{QTcF}$) in participants with HD was 6.6 ms (with an upper bound of the 90% CI 8 ms), which is not clinically meaningful. Pridopidine 45 mg BID is the dose to be tested in the HEALEY ALS Platform Trial. Although this was not a clinically meaningful QT effect, as there is no prior experience with pridopidine in the ALS patient population, we plan to include additional safety monitoring and risk mitigation measures.

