6.1 Analysis Sets

The ITT analysis set is henceforth referred to as the Full Analysis Set (FAS) and defined as follows:

- Full Analysis Set (FAS): Participants who were randomized within RGD plus placebo participants from specified regimens, classified according to their randomized treatment assignment. Participants who discontinue study drug but remain in the study will be included in the FAS. Observations completed after regimen data lock are excluded. Participants determined to not meet ALS diagnostic criteria are excluded.

The definition of the STF analysis set is revised as follows:

- Safety Full (STF) Set: Participants who initiated treatment within RGD plus placebo participants from specified regimens who are not known to be ineligible for RGD and who initiated treatment in their respective regimen, classified according to the treatment they actually received. Observations made after premature permanent discontinuation of study drug are included in this sample, should such participants remain on study. Observations completed after regimen data lock are excluded.

An analysis set restricting shared placebo participants to those regimens in which study drug is administered by the same route as RGD is defined as follows:

- Efficacy Common Mode of Administration (ECM) Set: The subset of participants in the FAS analysis set who are in regimens in which study drug is administered by the same route as RGD.

The definitions of the ECC, ERO, STN, and SRO analysis sets are the same as described in the M-SAP with reference to the ITT analysis set now referencing the FAS analysis set. The following analysis sets are specific to RGD:

- Modified Intention-to-treat (mITT) Set: Participants who were randomized within RGD plus placebo participants from specified regimens, who received at least one dose of study drug, and who completed at least one post-baseline ALSFRS-R assessment, classified according to their randomized treatment assignment. Participants who discontinue study drug but remain in the study will be included in the mITT. Observations completed after regimen data lock are excluded.

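### Delta-method intervals for adverse event rate differences break down when an arm has few or no events, which matters if they are reported in the 3:1 regimen-only safety set

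*SAP*

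**What the plan says.** SAP 6.6.1 takes over the TEAE analyses of the Master SAP with stated revisions. Two of them matter here:

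- "Treatment-dependent differences in the proportion of participants experiencing a given type of TEAE will not be tested".
- Between-arm contrasts of TEAE incidence, by contrast, "will be estimated as differences rather than ratios and will include comparison-wise 95% confidence intervals with variance estimates obtained by the delta method".

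The section gives no minimum event count, no rule for an arm without events, and no alternative interval. It does not name the analysis sets in which the intervals are reported. SAP 7.2 says only that analyses that fail because of small samples or non-convergence are left out with a comment.

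On the sets, SAP 6.1 states that "The definitions of the ECC, ERO, STN, and SRO analysis sets are the same as described in the M-SAP". It then lists the sets that take shared placebo participants from regimens A, B and C. STF and STN are on that list (STN from B and C only); the regimen-only safety set, SRO, is not. The arm sizes within the regimen come from the RSA Summary: "Participants will be randomized in a 3:1 ratio to active treatment or placebo (i.e., 120 active: 40 placebo").

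**The concern.** A delta-method interval for a rate difference takes its variance from the observed counts. When a count is zero, the estimated variance for that arm is zero, although the true uncertainty is large. With 40 placebo participants followed for about half a year, zero or one placebo event will be common for individual adverse event types.

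Under 3:1 allocation the small arm is the one likely to show no events by chance, so the error runs mainly one way: the active rate appears higher when it is not. For event types with no events in either arm, the interval claims certainty that the data do not hold. Since 6.6.1 rules out tests of proportions, the interval is the only between-arm inference that the section specifies. Cardiac events show how sparse the data can be: for PRIDE-HD, Protocol 5.11.1 reports "QT prolongation AEs: 0 in placebo, 2 in 45 mg BID".

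**Working it through.** The documents give no TEAE interval or coverage figure, so there is nothing to reproduce. The check applies the stated method to the planned design.

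**Inputs**
- Arm sizes 120 and 40 (RSA Summary).
- Follow-up 24 weeks each (RSA Summary), assuming no dropout: T1 = 120 × 168 / 365.25 = 55.2 and T0 = 40 × 168 / 365.25 = 18.4 person-years.
- Level 95%, z = 1.96: "comparison-wise 95% confidence intervals".
- Assumption: independent Poisson counts a (active) and b (placebo), with no repeat-event clustering.

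**Formula.** Difference d = a/T1 − b/T0; variance = a/T1² + b/T0²; interval d ± 1.96 × √variance.

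**Zero-event arm.** With b = 0 the lower limit is (k − 1.96√k)/T1. For k = 3 the bracket is 3 − 3.39 = −0.39; for k = 4 it is 4 − 3.92 = 0.08. Zero is therefore excluded from k = 4 onwards, whatever the person-time or allocation. With a = b = 0 the interval is 0 to 0.

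**Example, 4 versus 0**
- Delta method: 0.0725 per person-year (0.0015 to 0.1435).
- With 28 weeks of follow-up: 0.0621 (0.0012 to 0.1230).
- Given four events and equal rates, the chance that all fall on active is 0.75⁴ = 31.6%. The exact conditional two-sided p is 0.58.
- Zero events in 18.4 person-years is compatible with a rate of up to 3.689/18.4 = 0.20, well above the active estimate.
- Score interval: −0.136 to 0.186. MOVER with exact Poisson limits: −0.135 to 0.186.
- A log-link Poisson fit with the delta method reported convergence and gave the same 0.0015 to 0.1435.

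**Error rates at 120:40, equal true rates** (exact sums over Poisson pairs; the score statistic is d / √[pooled rate × (1/T1 + 1/T0)])

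| Expected active events | Delta coverage | Delta, false active higher | Delta, false active lower | Score coverage | Score, false active higher | Score, false active lower |
|---|---|---|---|---|---|---|
| 0.5 | 99.9% | 0.1% | 0.0% | 99.2% | 0.0% | 0.8% |
| 1 | 98.6% | 1.4% | 0.0% | 98.2% | 0.0% | 1.8% |
| 2 | 92.6% | 7.3% | 0.1% | 97.0% | 0.0% | 3.0% |
| 3 | 86.8% | 13.0% | 0.2% | 96.6% | 0.0% | 3.4% |
| 4 | 84.8% | 15.0% | 0.3% | 96.3% | 0.0% | 3.7% |
| 6 | 87.5% | 12.0% | 0.4% | 95.9% | 0.3% | 3.9% |
| 8 | 90.7% | 8.8% | 0.6% | 95.6% | 0.8% | 3.6% |

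The nominal rate on each side is 2.5%. At 4 expected active events the placebo arm shows none with probability exp(−4/3) = 26%. The high coverage in the first two rows counts the zero-width interval as correct, which it is only because the true difference was set to exactly zero.

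**With shared placebos.** The documents give no counts. Assuming 40 placebo participants in each of regimens A, B and C, the comparison is 120:160. Delta coverage is then 94.7% to 95.3% for 2 to 20 expected active events.

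**The case against.** The strongest objection is that much of this depends on the Master SAP. Section 6.6.1 names no analysis set and no rate model, and it inherits everything that it does not revise. That the regimen-only set is used for these intervals is an inference, and a sparse-event rule may already exist. This stands, and the conclusion is conditional on it.

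The variance formula is also assumed. With a participant-level robust variance, four events in two or three participants give an interval that includes zero. If the software treats an empty arm as a failure, SAP 7.2 would drop the interval. The fit above reported convergence, so that protection cannot be relied on.

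A reader might infer more than the documents support:

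- *That the intervals mislead in every safety set.* They do not. With shared placebos coverage is close to nominal; only the behaviour with an empty arm carries over.
- *That undercoverage grows as events become rarer.* At one or fewer expected active events, coverage is above nominal.
- *That these intervals alone carry the safety message.* SAP 6.6.1 to 6.6.3 also specify TEAE summaries by organ class and preferred term, laboratory grading and liver criteria, and the proportions meeting ECG stopping or monitoring rules.
- *That the protocol shows no QT or syncope events on placebo.* This is true of PRIDE-HD (Table 2). Table 1, for the whole safety database, shows 2 placebo participants with QT prolongation and 1 with syncope.

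**Conclusion.** The concern holds in conditional form. The stated method gives a zero-width interval for 0 versus 0 and excludes zero for any k versus 0 with k of at least 4. In a 120:40 comparison its coverage is about 85% to 93% for 2 to 8 expected active events, and the false active-higher rate peaks at 15% against 2.5%.

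This rests on simple Poisson counts, equal true rates, full 24-week follow-up, use of the regimen-only set for TEAE intervals, and the absence of a sparse-event rule in the Master SAP. Moving to 28 weeks leaves the threshold of 4 unchanged. The primary efficacy result and the other safety summaries are not affected. The plan should be changed, but the defect is limited to one set of safety intervals.

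**What to change.** First check the Master SAP for a sparse-event rule and for the sets in which TEAE rate differences are reported, and name those sets in 6.6.1. If there is no such rule, replace the delta-method interval with a score interval, or an exact-based one such as MOVER with exact Poisson limits, for the difference of two rates. Do this at least in regimen-only tables and wherever either arm has few or no events, and state what is shown for 0 versus 0. Where repeat events per participant are counted, use a participant-clustered variance only if the counts allow it.

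The cost is a change of SAP wording and one macro. There is also a statistical trade-off that should be stated. Intervals for rare events become wider. At 3:1 the score statistic for k versus 0 is √(k/3), which passes 1.96 only at k = 12, so the method is slower to flag a rare harm. Its remaining error leans slightly towards active lower: 3.0% to 3.9% for 2 to 8 expected active events, against 2.5%. For example, 0 active versus 2 placebo gives z = −2.45 and excludes zero, although that split has probability 0.25² = 6.25% given two events.
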